- Mean (average of triplicate measurements) QTc interval corrected using Fridericia's method (QTcF) \geq 480 ms at screening, or uncorrectable abnormalities in serum electrolytes (sodium, potassium, calcium, magnesium, and phosphorus)
- Left ventricular ejection fraction (LVEF) below the institutional lower limit of normal or below 50%, whichever is lower

Central Nervous System Exclusion Criteria

- Untreated or actively progressing CNS lesions (carcinomatous meningitis)

Patients with a history of CNS lesions are eligible, provided that all of the following criteria are met:

 - Measurable disease, per RECIST v1.1, must be present outside the CNS.
 - All known CNS lesions have been treated with radiotherapy or surgery.
 - CNS lesions have not been treated with whole-brain radiotherapy, except in patients who underwent definitive resection of or stereotactic therapy for all radiologically detectable parenchymal brain lesions.
 - Absence of interim progression must be confirmed by radiographic study within 4 weeks prior to initiation of study treatment. If new CNS metastases are suspected during the screening period, a confirmatory radiographic study is required prior to initiation of study treatment.
 - Any radiotherapy or surgery must be completed \geq 4 weeks prior to initiation of study treatment.
 - There is no ongoing requirement for corticosteroids, and any prior corticosteroid treatment must be discontinued \geq 2 weeks prior to initiation of study treatment. Treatment with an anticonvulsant at a stable dose is allowed.
 - No history of intracranial hemorrhage from CNS lesions
- History of metastases to brain stem, midbrain, pons, or medulla, or within 10 mm of the optic apparatus (optic nerves and chiasm)
- History of leptomeningeal metastatic disease

Additional Exclusion Criteria

- Current severe, uncontrolled systemic disease (including, but not limited to, clinically significant cardiovascular, pulmonary, or renal disease) other than cancer
- Anticipated use of any concomitant medication during or within 7 days prior to initiation of study treatment that is known to cause QT prolongation (which may lead to torsades de pointes)
- Uncontrolled diabetes or symptomatic hyperglycemia
- Any psychological, familial, sociological, or geographical condition that may hamper compliance with the protocol and follow-up after treatment discontinuation

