General guidance for dose modifications and treatment delays and discontinuation	
• The dose of cobimetinib and vemurafenib can be reduced by one dose level in the run-in period (see Section 5.1.5.1).• There will be no dose modifications for atezolizumab.• During the triplet combination period, Cycle 1 and beyond, the dose of cobimetinib can be reduced by 20 mg (one dose level) up to two times (i.e., from 60 mg to 40 mg and then from 40 mg to 20 mg). If further dose reduction is indicated after two dose reductions, the patient must discontinue cobimetinib but may continue treatment with atezolizumab and/or vemurafenib at the investigator's discretion.• During the triplet combination period, in order to preserve the blind, two reductions in tablet number will be allowed in both Arm A and Arm B. The first dose reduction will be from 3 tablets in the large bottle plus 1 tablet in the small bottle BID to 2 tablets in the large bottle plus 1 tablet in the small bottle BID; this will represent a true dose reduction in Arm A (from 960 mg BID to 720 mg BID) and in Arm B (from 720 mg BID to 480 mg BID). If a second dose reduction is required, patients in both arms will reduce from 2 tablets in the large bottle plus 1 tablet in the small bottle BID to 2 tablets in the large bottle BID. This will represent a true dose reduction in Arm A (from 720 mg BID to 480 mg BID) whereas in Arm B, because the small bottle contains placebo tablets, it will represent a "false" dose reduction (with dosing maintained at 480 mg BID). If further dose reduction is indicated after two dose reductions, the patient must discontinue vemurafenib but may continue treatment with atezolizumab and/or cobimetinib at the investigator's discretion.• If atezolizumab is withheld and corticosteroids are initiated for treatment of a toxicity, corticosteroids must be tapered over ≥ 1 month to ≤ 10 mg/day oral prednisone or equivalent before atezolizumab can be resumed. If atezolizumab is withheld for > 12 weeks, the patient should be discontinued from atezolizumab. Study treatment may be withheld for > 12 weeks to allow for patients to taper off corticosteroids prior to resuming treatment. Atezolizumab can be resumed after being withheld for > 12 weeks for patients experiencing clinical benefit as determined by the investigator. The Medical Monitor is available to advise as need.• If either cobimetinib or vemurafenib is withheld for > 28 days because of toxicity, the patient should be discontinued from that drug, unless resumption of treatment is approved by the investigator. The Medical Monitor is available to advise as needed.• After dose reduction, consideration may be given to allow for dose escalation of cobimetinib or vemurafenib by a maximum of one dose level following resolution of the adverse event that resulted in dose modification, provided there are no safety concerns (see Section 5.1.5.2). Escalation is not permitted during the run-in period (see Section 5.1.5.1).

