^b Atezolizumab may be withheld for a period of time beyond 12 weeks to allow for corticosteroids to be reduced to \leq 10 mg/day oral prednisone or equivalent.

The acceptable length of the extended period of time must be based on an assessment of the benefits and risks by the investigator and in alignment with the protocol requirements for the duration of treatment and documented by the investigator. The Medical Monitor is available to advise as needed.

^c Resumption of atezolizumab may be considered in patients who are deriving benefit and have fully recovered from the immune-mediated event. The decision to re-challenge patients with atezolizumab should be based on *the* investigator's benefit–risk *assessment* and documented by the investigator (or an appropriate delegate). The Medical Monitor is available to advise as needed.

Table 3 Guidelines for Management of Patients Who Experience Specific Adverse Events (cont.)

Event	Action to Be Taken
QT interval prolongation	
QTcF \leq 500 ms with change from baseline in QTcF of <60 ms	
Continue all study treatment.
QTcF > 500 ms with change from baseline in QTcF of <60 ms or QTcF \leq 500 ms with change from baseline in QTcF of \geq 60 ms	
Withhold vemurafenib. Continue atezolizumab and cobimetinib.Rule out other risk factors for arrhythmia (e.g., myocardial ischemia). Check for electrolyte disturbances (e.g., potassium, magnesium, and calcium).Evaluate concomitant medications to determine if there is co-administration of drugs that prolong QT interval.Refer patient to cardiologist.Monitor ECG weekly.If QTcF improves to \leq 500 ms or baseline within 28 days, resume vemurafenib with dose reduced by one level. Repeat ECG at 2 and 4 weeks after resuming vemurafenib, on Day 15 of each subsequent cycle for three cycles, and then every 3 months thereafter.If QTcF does not improve to \leq 500 ms or baseline within 28 days, permanently discontinue vemurafenib.

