QTcF > 500 ms with change from baseline in QTcF of \geq 60 ms	
Permanently discontinue vemurafenib. Continue atezolizumab and cobimetinib.Rule out other risk factors for arrhythmia (e.g., myocardial ischemia). Check for electrolyte disturbances (e.g., potassium, magnesium, and calcium).Evaluate concomitant medications to determine if there is co-administration of drugs that prolong QT interval.Refer patient to cardiologist.Monitor ECG weekly until QTcF improves to \leq 500 ms or baseline.

QTcF = QT interval corrected using Fridericia's formula.

- ^a If corticosteroids have been initiated, they must be tapered over \geq 1 month to \leq 10 mg/day oral prednisone or equivalent before atezolizumab can be resumed.
- ^b Atezolizumab may be withheld for a period of time beyond 12 weeks to allow for corticosteroids to be reduced to \leq 10 mg/day oral prednisone or equivalent. The acceptable length of the extended period of time must be based on an assessment of the benefits and risks by the investigator and in alignment with the protocol requirements for the duration of treatment and documented by the investigator. The Medical Monitor is available to advise as needed.
- ^c Resumption of atezolizumab may be considered in patients who are deriving benefit and have fully recovered from the immune-mediated event. The decision to re-challenge patients with atezolizumab should be based on *the* investigator's benefit-risk *assessment* and documented by the investigator (or an appropriate delegate). The Medical Monitor is available to advise as needed.

Table 3 Guidelines for Management of Patients Who Experience Specific Adverse Events (cont.)

Event	Action to Be Taken
Asymptomatic LVEF decrease from baseline	
LVEF \geq 50% or LVEF 40%–49% with < 10% absolute decrease from baseline	
Continue all study treatment.

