- z At screening, patients will be tested for HIV, HBsAg, HBsAb, total HBcAb, and HCV antibody. If a patient has a negative HBsAg test and a positive total HBcAb test at screening, an HBV DNA test should be performed. If a patient has a positive HCV antibody test at screening, an HCV RNA test must also be performed to determine if the patient has an active HCV infection.

Appendix 1

Schedule of Activities (cont.)

- ^{aa} For women of childbearing potential, a serum pregnancy test is required at screening (within 7 days prior to Run-In Day 1) and at the treatment discontinuation visit. Urine pregnancy tests will be performed on Day 1 (or within 7 days) of every cycle (e.g., Day 1 of Cycles 1, 2, 3 etc.). If a urine pregnancy test is positive, it must be confirmed by a serum pregnancy test. A woman is considered to be of childbearing potential if she is postmenarcheal, has not reached a postmenopausal state (≥ 12 continuous months of amenorrhea with no identified cause other than menopause), and has not undergone surgical sterilization (removal of ovaries and/or uterus).
- ^{bb} Both blood glucose and lipid panel must be obtained after at least an 8-hour fast, at screening only. Lipid panel should include total cholesterol, low-density lipoprotein, and triglycerides.
- ^{cc} ECG recordings will be obtained at screening. ECG recordings will be obtained prior to the morning doses of cobimetinib and vemurafenib on Run-In Day 15 (± 3 days); on Day 15 (± 3 days) of Cycles 1, 2, 3, and every three cycles thereafter (i.e., Day 15 of Cycles 6, 9, 12, etc.) (± 3 days); at the treatment discontinuation visit (± 3 days); and as clinically indicated. EGCs should be performed prior to other procedures scheduled at that same time (e.g., vital sign measurements, blood draws unless pre-authorized by the Medical Monitor) and after the patient has been resting in a supine position for at least 10 minutes (see Section 4.5.6.3 for additional details). If vemurafenib is discontinued and study treatment (cobimetinib and/or atezolizumab/atezolizumab placebo) continues, ECGs are required as per standard of care or as clinically indicated. If atezolizumab/atezolizumab placebo treatment is interrupted or discontinued, ECGs may be performed at the Day 1 visit of the following cycle.

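### Protocol Table 3, second QT row: two different vemurafenib holds share one resume and 28-day stop target, and for the hold on a rise of 60 ms or more the 500 ms part of that target is already met when the hold starts

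*Protocol*

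**What the plan says.** The QT block of Table 3 (Protocol Section 5.1.5.4) has three rows.

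- **First row:** QTcF at or below 500 ms and a change from baseline below 60 ms. All drugs carry on.
- **Second row:** two findings joined by *or*. It begins "QTcF > 500 ms with change from baseline in QTcF of <60 ms or QTcF" and goes on to QTcF at or below 500 ms with a change of 60 ms or more. Vemurafenib is withheld; the other two drugs continue.
- **Third row:** both limits crossed. Vemurafenib is stopped permanently.

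The second row has one restart instruction and one stop instruction. If QTcF improves to at or below "500 ms or baseline within 28 days, resume vemurafenib with dose reduced by one level". If it does not improve to at or below "500 ms or baseline within 28 days, permanently discontinue vemurafenib". No footnote, separate bullet or linking word ties either part of the target to either finding.

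The third row uses the same target for one combined finding, and only to end surveillance: "Monitor ECG weekly until QTcF improves to" that level.

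**The concern.** A hold, its release and its time limit should refer to the same abnormality. For the first trigger they do. For the second, the abnormality is the rise from baseline, while the first part of the release target is an absolute value the patient has not exceeded. Taken literally, one ECG can satisfy both the instruction to withhold and the instruction to resume, and the 28-day stop has nothing to act on.

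QT prolongation is listed among the identified risks of vemurafenib (Section 5.1.3) and described as exposure-dependent, with a possible path to torsades de pointes (Section 5.1.3.6). Two sites could therefore restart the drug or withdraw it permanently on identical ECGs, each able to point to the table.

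**Working it through.** **Inputs.** The thresholds are those of the three rows above. Section 4.1.2 excludes a mean QTcF at or above "480 ms at screening, or uncorrectable abnormalities in serum electrolytes", so screening QTcF is below 480 ms. Table 3 does not define baseline. Appendix 1, footnote cc, says "ECG recordings will be obtained at screening", and the next scheduled ECG is Run-In Day 15. I therefore take baseline as the screening value; this is an assumption. Write B for baseline, Q for current QTcF and D = Q − B.

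**Step 1, first trigger (Q > 500, D < 60).** B = Q − D > 500 − 60 = 440. Once Q is at or below 500, D ≤ 500 − B < 60. The 500 ms target clears both limits, so it serves this trigger well. Since B < 480, the baseline part adds nothing here.

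**Step 2, second trigger (Q ≤ 500, D ≥ 60).** B = Q − D ≤ 500 − 60 = 440. Q ≤ 500 is part of the trigger, so on a literal *or* the resume condition is true from the start whatever D is. The 28-day stop needs Q above 500. But with B ≤ 440, Q above 500 gives D > 500 − 440 = 60, which is the third row and an immediate permanent stop. The literal 28-day stop therefore has no case of its own.

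**Step 3, the two readings compared.** The literal reading applies either part of the target to either trigger. The paired reading applies 500 ms to the first trigger and baseline to the second. Take B = 420 and a hold at Q = 490 (D = 70). On day 28 Q = 470 (D = 50). Literal: restart one level lower. Paired: permanent discontinuation.

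More generally, for whole-millisecond QTcF on day 28 of a second-trigger hold:

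| Baseline (ms) | Above baseline, rise under 60 | Rise still 60 or more, QTcF within 500 | Width of disagreement (500 − B) |
|---|---|---|---|
| 380 | 381–439 | 440–500 | 120 |
| 410 | 411–469 | 470–500 | 90 |
| 440 | 441–499 | 500 only | 60 |

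Literal: restart permitted in both middle columns. Paired: permanent stop in both. The third column is the safety problem, because there the row's own hold condition is still met at restart. These widths show what the wording decides. They are not patient frequencies.

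**Step 4, is the target settled elsewhere?** Section 4.5.6.3 refers to 5.1.3.6, which refers to Table 3. Section 5.1.5.1 asks for improvement during the run-in but gives no QT value. Section 5.1.5.3 and the general guidance row of Table 3 limit the length of a hold without defining recovery. The SAP has no QT management rule.

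**The case against.** The strongest reply is that the paired reading is what any clinician would take from the row. A patient already within 500 ms cannot improve to that level, the two findings and the two targets appear in the same order, and the literal reading makes the row contradict itself. I accept that this is the more natural intent. It remains an inference, and a demanding one: a patient whose rise fell from 70 to 10 ms would be permanently stopped at day 28, although the first row would let that ECG pass. The third row's use of the same phrase settles nothing, since it has one combined finding and the drug is already stopped.

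A second reply is that other rules contain the risk, and they do.
- During a hold there are a search for other causes, cardiology referral and weekly ECGs.
- Restart is one dose level lower, followed by "Repeat ECG at 2 and 4 weeks after resuming vemurafenib, on Day 15 of each subsequent cycle for three cycles" and then every 3 months. A persisting rise of 60 ms or more at the 2-week ECG would bring the hold back.
- In the run-in, toxicity that does not improve within 28 days of reduction or interruption leads to discontinuation unless the Medical Monitor approves resumption (Section 5.1.5.1).
- Vemurafenib must stop if more reduction is needed after two reductions (Section 5.1.5.2 and the general guidance row).
- Section 4.5 requires an acceptable clinical assessment before dosing, and Section 5.1.5.4 preserves clinical judgment.

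None of these says which part of the target governs.

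Third, the day-28 comparison is somewhat artificial: on the literal reading a restart could come much earlier, and a QTcF still raised after 28 days off drug is the less expected course for an exposure-dependent effect. Section 4.4.4.2 reports no mean QTc change above 20 ms among 132 patients. Those are means and do not exclude individual outliers.

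Three stronger inferences are not supported. A reader might infer that the plan intends restart into unresolved prolongation; the word order and the verb point the other way. A reader might infer endless hold-and-restart cycles; the two-reduction cap prevents that. A reader might infer that restart in Arm B is at an unreduced dose; the first step is a real reduction in both arms, and only Arm B's second step is a nominal "dose reduction (with dosing maintained at 480 mg BID".

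**Conclusion.** The point stands as a minor safety-rule correction. For the hold on a rise of 60 ms or more, the row read literally permits restart with the triggering rise unresolved, and its 28-day stop cannot apply while QTcF stays within 500 ms. The sensible alternative is left unwritten. The first trigger is unaffected.

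The finding that the 500 ms part is met at the start follows from the trigger's definition and needs no assumption about baseline. The screening-value assumption matters only for saying that the baseline part adds nothing on a literal reading. How many patients would be affected is unknown.

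It does not follow that trial results are at risk: efficacy is analysed in all randomized patients as assigned (SAP Section 4.4), and no analysis definition uses this row.

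**What to change.** Split the target by trigger.

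- **QTcF above 500 ms with a change below 60 ms:** keep resumption one level lower at QTcF at or below 500 ms, and the 28-day stop as it is.
- **QTcF at or below 500 ms with a change of 60 ms or more:** state that vemurafenib must not resume while the change is 60 ms or more, and that it is permanently discontinued if this has not resolved within 28 days. If full return to baseline was intended, write that stricter target instead.

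The sponsor's safety physicians should confirm which they meant before the edit. The bar on restart forbids nothing that the paired reading allows, but used as the whole resume criterion it would be looser than return to baseline. The asymptomatic LVEF row of Table 3 is a model: it too combines an absolute value with a change from baseline, yet it states its restart and stop limits explicitly.

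The cost is one row in the next amendment, or a memo to sites. Compared with the literal reading, holds for this trigger would be somewhat longer, with possibly a few more 28-day stops.

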LVEF <40% or LVEF 40%–49% with \geq 10% absolute decrease from baseline	
Withhold cobimetinib for at least 2 weeks. Continue atezolizumab and vemurafenib.Re-evaluate LVEF at 14 days. If patient has a < 10% absolute decrease from baseline in LVEF, for the first occurrence resume cobimetinib with dose reduced by one level to 40 mg; for the second occurrence, resume cobimetinib at 20 mg; and for the third occurrence, permanently discontinue cobimetinib^d. For all patients restarting treatment, re-evaluate LVEF at 2, 4, 10, and 16 weeks and then every 12 weeks (3 cycles as per protocol) or as clinically indicated until treatment discontinuation. If patient has an LVEF of <40% or a \geq 10% absolute decrease from baseline, permanently discontinue cobimetinib. 
For patients who permanently discontinue cobimetinib:
 
LVEF assessments should continue post-treatment every 6 weeks or as clinically indicated until the LVEF recovers to LLN or 50%.

LLN = lower limit of normal; LVEF = left ventricular ejection fraction.

- If corticosteroids have been initiated, they must be tapered over \geq 1 month to \leq 10 mg/day oral prednisone or equivalent before atezolizumab can be resumed.
- Atezolizumab may be withheld for a period of time beyond 12 weeks to allow for corticosteroids to be reduced to \leq 10 mg/day oral prednisone or equivalent. The acceptable length of the extended period of time must be based on an assessment of the benefits and risks by the investigator and in alignment with the protocol requirements for the duration of treatment and documented by the investigator. The Medical Monitor is available to advise as needed.
- Resumption of atezolizumab may be considered in patients who are deriving benefit and have fully recovered from the immune-mediated event. The decision to re-challenge patients with atezolizumab should be based on *the* investigator's benefit–risk *assessment* and documented by the investigator (or an appropriate delegate). The Medical Monitor is available to advise as needed.
- Patients on a cobimetinib dose less than 60 mg will reduce by one dose level reduction (a 20-mg daily reduction), from a 40-mg daily dose to a 20-mg daily dose, and patients on a 20-mg daily dose at the time of the interruption (for LVEF decline) should discontinue cobimetinib.

Table 3 Guidelines for Management of Patients Who Experience Specific Adverse Events (cont.)

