Event	Action to Be Taken
Symptomatic LVEF decrease from baseline	
	
Withhold cobimetinib for at least 4 weeks. Continue atezolizumab and vemurafenib.Patient referral to cardiologist is strongly recommended.Re-evaluate LVEF at 28 days. 
If the patient is asymptomatic following the treatment break:
 
If patient has a < 10% absolute decrease from baseline in LVEF, for the first occurrence resume cobimetinib with dose reduced by one level to 40 mg; for the second occurrence, resume cobimetinib at 20 mg; and for the third occurrence, permanently discontinue cobimetinib ^a. For all patients restarting treatment, re-evaluate LVEF at 2, 4, 10, and 16 weeks and then every 12 weeks (3 cycles as per protocol) or as clinically indicated until treatment discontinuation.If patient has an LVEF of < 40% or a ≥ 10% absolute decrease from baseline, permanently discontinue cobimetinib. 
If the patient remains symptomatic following the treatment break:
 
Permanently discontinue cobimetinib. 
For patients (asymptomatic and symptomatic) who permanently discontinue cobimetinib:
 
LVEF assessments should continue post-treatment every 6 weeks or as clinically indicated until the LVEF recovers to LLN or 50% and or symptoms resolve.

LLN = lower limit of normal; LVEF = left ventricular ejection fraction.

- ^a If corticosteroids have been initiated, they must be tapered over ≥ 1 month to ≤ 10 mg/day oral prednisone or equivalent before atezolizumab can be resumed.
- ^b Atezolizumab may be withheld for a period of time beyond 12 weeks to allow for corticosteroids to be reduced to ≤ 10 mg/day oral prednisone or equivalent. The acceptable length of the extended period of time must be based on an assessment of the benefits and risks by the investigator and in alignment with the protocol requirements for the duration of treatment and documented by the investigator. The Medical Monitor is available to advise as needed.
- ^c Resumption of atezolizumab may be considered in patients who are deriving benefit and have fully recovered from the immune-mediated event. The decision to re-challenge patients with atezolizumab should be based on *the investigator's benefit–risk assessment* and documented by the investigator (or an appropriate delegate). The Medical Monitor is available to advise as needed.

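### In Table 3 the cobimetinib resume rule omits the 40% LVEF floor, so for an eligible baseline below 50% it can contradict the permanent-stop rule (minor)

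*Protocol*

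**What the plan says.** Protocol Section 5.1.5.4, Table 3, has one block for asymptomatic and one for symptomatic LVEF decrease from baseline.

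- **Continue row (asymptomatic).** All study treatment continues if LVEF is 50% or more, or in the case "LVEF 40%–49% with < 10% absolute decrease from baseline". The change limit is paired with a 40% floor.
- **Hold row (asymptomatic).** The trigger begins "LVEF <40% or LVEF 40%–49% with", the second part being completed by a fall of at least 10 points. Cobimetinib is held for at least 2 weeks and LVEF is repeated at 14 days.
- **Resume rule at re-check.** "If patient has a < 10% absolute decrease from baseline in LVEF, for the first occurrence resume cobimetinib with dose reduced by one level". A second occurrence resumes at 20 mg, "and for the third occurrence, permanently discontinue cobimetinib".
- **Stop rule at re-check.** An LVEF under 40% or a fall of 10 points or more leads to the opposite action: "absolute decrease from baseline, permanently discontinue cobimetinib".
- **Symptomatic block.** The hold is at least 4 weeks, with a re-check at 28 days. Patients who are then free of symptoms face the same pair of rules, the first opening "If patient has a < 10% absolute decrease from baseline in LVEF". The other branch, "If the patient remains symptomatic following the treatment break", always ends in permanent discontinuation.

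Footnote d stops patients already on 20 mg. Section 5.1.5.2 bars re-escalation from 40 to 60 mg. Section 4.1.2 excludes a baseline LVEF below the lower of the institutional LLN and 50%. Neither the footnotes nor the general guidance in Table 3 ranks the resume rule against the stop rule.

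**The concern.** The two re-check rules are written as separate conditions, and nothing such as 'otherwise' or 'regardless' links them. The stop rule contains an absolute floor and a change limit. The resume rule contains only the change limit. A patient whose LVEF is under 40% but has fallen by less than 10 points satisfies both, and the instructions are opposite: restart at a lower dose, or never restart.

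The asymptomatic block shows the effect most clearly. Its under-40% hold trigger carries no change condition. A patient can therefore be held for an LVEF that already satisfies the resume limit on the day the hold starts, and still satisfies it on day 14 without any recovery.

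At stake is the clarity of a safety rule for a drug whose identified risks include left ventricular dysfunction (Section 5.1.2).

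**Working it through.** There is no figure in the plan to reproduce. The check is on the logic of the rules.

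**Inputs.** Let b be baseline LVEF and r the re-check LVEF, both in percentage points.

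- Resume (Table 3, both blocks): b − r < 10.
- Stop (Table 3, both blocks): r < 40, or b − r ≥ 10.
- Eligible (Section 4.1.2): b ≥ min(LLN, 50).

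**Where both apply.** The second limb of the stop rule is the exact complement of the resume rule, so overlap can arise only through r < 40. Both apply when

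b − 10 < r < 40.

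This requires b − 10 < 40, that is b < 50. The band is 40 − (b − 10) = 50 − b points wide.

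**Example.** b = 47, r = 39. The fall is 47 − 39 = 8, which is under 10, so resume. But 39 is under 40, so stop.

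**Size of the band by baseline.**

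| Baseline | Band width (points) | Whole-point re-checks meeting both rules |
|---|---|---|
| 50 or more | 0 | none |
| 49 | 1 | none |
| 48 | 2 | 39 |
| 47 | 3 | 38–39 |
| 46 | 4 | 37–39 |
| 45 | 5 | 36–39 |

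**By institutional LLN.** The documents give no site LLN, so this is an assumption shown as a range, counting whole-point pairs of baseline and re-check:

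- LLN of 50 or more: 0 pairs.
- LLN of 48: 1 pair (48 and 39).
- LLN of 45: 4 + 3 + 2 + 1 = 10 pairs.
- LLN of 40: 9 + 8 + … + 1 = 45 pairs.

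These count LVEF readings, not patients.

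**By occurrence and dose.** There are 3 × 3 = 9 states (first, second or third occurrence; 60, 40 or 20 mg).

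- Third occurrence always stops: 3 states removed.
- 20 mg at a first or second occurrence stops by footnote d: 2 removed.
- A second occurrence on 60 mg cannot be reached, because the first reduces the dose and escalation from 40 to 60 mg is barred: 1 removed.

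That leaves 9 − 6 = 3: first occurrence on 60 mg, first on 40 mg, second on 40 mg. In the symptomatic block the patient must also be symptom-free after the break.

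**Check of the fix.** If resume becomes r ≥ 40 and b − r < 10, it is the exact logical complement of r < 40 or b − r ≥ 10. Every reading then meets one rule and only one. The only readings whose instruction changes are those with b − 10 < r < 40.

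**The case against.** The strongest reply is that the stop rule settles the case itself. For a baseline of 50% or more, an LVEF under 40% is already a fall of more than 10 points, so the change limb alone would stop the drug. At the re-check the under-40% limb does independent work only when the fall is less than 10 points, which is exactly the disputed band. If resume prevailed there, that limb would have no effect. This stands as evidence of intent: the sponsor meant a floor, and the continue row uses the same one. It does not remove the contrary instruction in the resume sentence.

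A reader might go further and infer that the stop rule governs only after restart, because in the asymptomatic block it follows the monitoring sentence that begins "For all patients restarting treatment, re-evaluate LVEF at 2, 4, 10, and 16 weeks". The documents do not support this. In the symptomatic block the stop rule is a bullet of its own at the re-check. In the asymptomatic block, that reading would leave a patient with a fall of 10 points or more at day 14 with no instruction.

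It is also fair to say that Section 5.1.5.4 presents Table 3 as guidance that leaves room for clinical judgment, that cardiology referral is strongly recommended in symptomatic cases, and that any restarted patient has LVEF repeated at 2 weeks, when a value under 40% would trigger the hold again. These points limit the consequence of a wrong choice and support a low severity. They do not decide which instruction applies at the re-check.

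**Conclusion.** The resume rule is wrong as written, and the point is minor. In both blocks, for an eligible baseline below 50%, a re-check under 40% and less than 10 points below baseline receives two opposite instructions with no stated precedence. For baselines of 50% or more the rules do not overlap.

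A reader might infer that some patients will certainly be caught by this. The documents do not support any count. The conflict needs a site with an LLN below 50%, and no LLN is stated. It also needs a re-check inside a narrow band and one of the three occurrence-by-dose states. The number affected may be zero. Nor do the documents support reading Table 3 as a deliberate policy of restarting below 40%, since the stop rule points the other way.

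No endpoint, analysis or comparison between arms is affected. The logic follows directly from the stated thresholds. The only assumption is the LLN range used to show the size of the band.

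**What to change.** In both LVEF blocks of Table 3, change the resume condition to an LVEF of at least 40% together with an absolute decrease from baseline of less than 10%. This is the floor the continue row already uses. An LVEF under 40% at re-evaluation would then always mean permanent discontinuation.

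The cost is one added phrase in each of two table cells at the next amendment. No new assessment is needed, no other threshold moves, and nothing changes for any patient with a baseline of 50% or more.
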